## **4 SELECTION OF SUBJECTS AND CENTRES**

### **4.1 Number of Subjects**

As calculated in section 9.1, Sample Size Calculation, 776 subjects should be enrolled in the clinical trial, i.e. 388 subjects per treatment group.

## 4.2 Sites

The study will be conducted on a multinational and multicenter basis. It is intended that the study will take place at approximately 30 sites.

## 4.3 General Criteria for Subjects' Selection

All adult patients with unruptured saccular aneurysms will be considered for trial inclusion, if it is decided that the risk of preventive aneurysm repair outweighs the risk of aneurysm rupture, based on the individual centres' policy. Irrespective of this management decision, there will be no further selection based on all other patient- or aneurysm-characteristics.

## 4.4 Inclusion Criteria

Subjects meeting all of the following criteria will be considered for admission to the trial:

- Patient with at least one intradural, saccular unruptured aneurysm in whom it is decided not to intervene with preventive neurosurgical or endovascular aneurysm repair and who are monitored on a regular basis for aneurysm growth
- 18 years or older
- Last aneurysm imaging with either CTA/MRA within the last 3 months
- Ability of subject to understand character and individual consequences of clinical trial
- Not legally incapacitated
- Written informed consent (must be available before enrolment in the trial)
- For women with childbearing potential adequate contraception.

## 4.5 Exclusion Criteria

Subjects presenting with any of the following criteria will not be included in the trial:

- All non-saccular UIAs or aneurysms related to arteriovenous malformations
- Daily ASA already prescribed for another indication
- Use of a vitamin K antagonist or direct oral anticoagulant (DOAC) treatment at baseline
- History of hypersensitivity/allergy to ASA or to any other drug with similar chemical structure or to any excipient present in the pharmaceutical form of ASA
- History of asthma induced by salicylates or other anti-inflammatory drugs
- Other contra-indications for ASA not yet mentioned in the dosage of 81-100 mg/day (e.g. bleeding disorders, gastric ulcers and/or intestinal ulcers, acute liver failure of kidney failure, severe heart failure, treatment with methotrexate in a dosage 15 mg/week or above)
- Use of another platelet aggregation inhibitor, which in combination with ASA would give an unacceptable risk of side effects/complications
- Chronic kidney disease stage IV and V (GFR <30mL/min/1.73m^2)
- Pregnancy and lactation
- Participation in another interventional clinical trial
- Life-expectancy <3 years

|   |   |                               |
|---|---|-------------------------------|
| Clinical Trial Code: Protect-U
EudraCT: 2017-000514-35 | Trial Protocol
Version 07 - August 23 - 2022 | Page 28 of 62
CONFIDENTIAL |
|---|---|-------------------------------|

No subject will be allowed to enrol in this trial more than once.

## 4.6 Criteria for Withdrawal

### 4.6.1 Withdrawal of Patients from Treatment

Any patient can withdraw from the treatment at any time without personal disadvantages and without having to give a reason. Patients who discontinue participation in the clinical study on their own or patients who are withdrawn by the investigator, for reasons other than disease progression (i.e. in case of AEs, protocol violations), will be defined as premature withdrawals. Withdrawn patients will be asked to attend a final follow-up visit and to return unused trial medication. Premature withdrawals will not be replaced. The time of treatment discontinuation must be documented in the patient file and on the CRF.

The investigator can also discontinue the participation of a patient in the study after considering the risk-to-benefit ratio, if he/she no longer considers the further treatment of the patient according to study protocol justifiable. The date of and the primary reason for the withdrawal, as well as the observations available at the time of withdrawal, are to be documented on the CRF. Reasons leading to the withdrawal of a patient can include the following (**one primary reason must be determined**):

- **Lack of efficacy** of the experimental intervention
- **Intolerable adverse events** from **both** components of the intervention (intensive blood pressure control **and** ASA-medication), e.g.
  - Any bleeding that results in hospital inpatient treatment
  - Severe skin reaction and/or asthma requiring treatment with medication exceeding a single dose
  - Gastric ulcer, if not possible to manage by gastroprotective co-medication
  - Severe orthostatic hypotension
- Disease progression
  - In patients with 1 intracranial aneurysm, end of treatment applies if aneurysm rupture (SAH) occurs or interventional treatment of the aneurysm (endovascular or neurosurgical). Patients who have multiple aneurysms can stay in the trial if growth, rupture or preventive treatment of 1 aneurysm occurs
- **Lack of patient's cooperation**, e.g.
  - Patient's request to withdraw
  - Lack of compliance, patient fails to attend the interim visits as agreed or perform self-medication according to schedule
- **Other reasons** (noting reason), e.g.
  - Other diagnosis than study disease
  - Did not meet major in-/exclusion criteria (coming to light after randomisation)
- Existing or intended pregnancy, lactation in patients of the intervention group. If patients in the control group become subsequently pregnant and/or need to breastfeed after randomisation, they will not be excluded from the trial.

All patients who finish the study prematurely will be asked to attend a follow-up visit and to return unused trial medication. The patient must be asked to consent to this last examination. The withdrawal examination will be documented in the CRF.

If a patient does not come to a visit, the patient will be contacted and asked for information. If the patient wants to withdraw and agrees to give explaining reasons, the reason should be documented in the patients file and in the CRF.

In case of early withdrawal, the last aneurysm imaging will be used for the primary outcome analysis (*last observation carried forward*).

If a patient has severe side effects from one component of the intervention only, (e.g. severe orthostatic hypotension from intensive blood pressure control or major gastrointestinal bleeding from ASA), it can be decided to adjust or stop the component of the intervention causing the side effects, while continuing the other component of the intervention.

For documentation of AEs and SAEs see 8.1.6 and 8.2.

| Term                         | Definition   | Comment/ Sample  |
|------------------------------|--|--|
| Drop-out, study              | 
Participation terminated completely, including follow-up
 
Possible reasons:
 
 
• Patient withdraws consent: Withdrawal
 
• Patient moved/cannot be contacted
 
• Interventions cannot be performed due to medical reasons
 
• Non-compliance of patient
 
 
Drop-out after completion of study intervention:
Lost to follow-up
 
Final examination will be performed, if patient agrees. Study-Completion/ Withdrawal-form will be completed.
 | 
ITT-sample
 
ITT-sample (if study intervention completed)
  |
| Drop-out, study intervention | Termination of study intervention, follow-up once as per protocol.   | ITT  |
| Screening-failure            | 
Exclusion criteria given prior to screening / enrolment:
 
Patient will be recorded at screening list, but will not be provided with a patient number.
   | -  |
| Protocol deviation           | 
Drop-out to study and drop-out to study intervention are both protocol deviations.
 
Major deviations:
 
If exclusion criteria become evident after enrollment, and safety of the participant is affected, or if the diagnosis does not any more relate to the indication listed in the protocol affecting the benefit/risk negatively, the participant has to be excluded from study intervention. FU-examinations may still be performed.
 
Minor deviations:
  | 
ITT (assessment of protocol deviations by LKP/ PI together with Biometrician)
 
ITT-analysis (if minor deviations)
 |

|   |   |                               |
|---|---|-------------------------------|
| Clinical Trial Code: Protect-U
EudraCT: 2017-000514-35 | Trial Protocol
Version 07 - August 23 - 2022 | Page 30 of 62
CONFIDENTIAL |
|---|---|-------------------------------|

|  |  |  |
|--|--|--|
|  | Other protocol deviations (errors in timing of visits/ missing samples/ missing examinations) do not result in exclusion |  |
|--|--|--|

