## CLINICAL TRIAL SCHEDULE

| Visit No.                                    | Visit 0                      | Visit 1        | Visit 2              | Visit 3 - 20               | Visit 21                                      | Visit 22  |
|--|------------------------------|----------------|----------------------|----------------------------|---|---|
|  | Screening*                   | Baseline       | Treatment phase      |                            | End of treatment/
study                    | Follow-up   |
| Day  | 0 – 30 days prior to visit 1 | Day 0          | 6 months +/- 30 days | every 6 months +/- 30 days | Month 36 +/- 30 days or month 120 +/- 30 days | 30 +/- 10 days after end of treatment visit (or after withdrawal) |
| Procedure                                    |                              |                |                      |                            |   |   |
| Written informed consent                     | ● (S)**                      |                |                      |                            |   |   |
| Inclusion/ exclusion criteria                | ● (S)                        | ●              |                      |                            |   |   |
| Demographic data, vital signs                | ●                            |                |                      |                            |   |   |
| Medical history                              | ● (R)**                      |                |                      |                            |   |   |
| Smoking status and alcohol consumption       | ●                            | ●              | ●                    | ●                          | ●   | ●   |
| Randomization                                |                              | ●              |                      |                            |   |   |
| Pregnancy test                               | ●  (S)           | ●  |                      |                            |   |   |
| Concomitant medication                       | ● (R)                        | ●              | ●                    | ●                          | ●   | ●   |
| AE   |                              | ●              | ●                    | ●                          | ●   | ●   |
| Aneurysm/ baseline characteristics           |                              | ●              |                      |                            |   |   |

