## 5.6 Blinding

This is an open trial, in which patients and investigators are not blinded. However, there will be an examiner-blinded assessment of images, therefore no information of patient allocation using patient ID-numbers or other data that would unblind the allocation of a patient to one of the two trial arms should be made available prior to the imaging analysis.

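### Section 4.6.1 allows exits from the study that only intervention patients can meet, then carries the last image forward, without clearly requiring collection of later standard-of-care scans; the likely bias is small and cheap to prevent.

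*Protocol*

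**What the plan says.** Section 5.6 states: "This is an open trial, in which patients and investigators are not blinded". Only the reading of images is blinded.

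Section 4.6.1 is headed as withdrawal from treatment, but its operative sentence goes further: "The investigator can also discontinue the participation of a patient in the study after considering the risk-to-benefit ratio". The first reason listed is "Lack of efficacy of the experimental intervention", with no criterion or example; disease progression is a separate item. The list also contains intolerable adverse events from both components of the intervention. Pregnancy is a reason in the intervention group only, since the section says that control patients who become pregnant stay in the trial.

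On what follows an exit, the same section says: "Withdrawn patients will be asked to attend a final follow-up visit and to return unused trial medication". It adds: "The patient must be asked to consent to this last examination". The Clinical Trial Schedule places this contact at "30 +/- 10 days after end of treatment visit (or after withdrawal"). For the primary endpoint: "In case of early withdrawal, the last aneurysm imaging will be used for the primary outcome analysis", which the section labels last observation carried forward. The table of terms in 4.6.1 separates a drop-out from the study, where follow-up ends too, from a drop-out from the intervention, which is followed up once. For patients found ineligible after enrolment it says "FU-examinations may still be performed".

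Section 6 expects patients to remain on the intervention until three years after the last enrolment, even after the primary endpoint. Section 9.3 promises an intention-to-treat analysis of all randomised patients.

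**The concern.** The primary endpoint is rupture or growth by month 36±6, and growth is known only from images that reach the central readers. Blinded reading protects against biased interpretation of a scan. It does nothing for a scan that is never uploaded.

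Carry-forward applies to both arms, but three of the listed routes to early exit are open only to the intervention arm. One of them, lack of efficacy, is undefined and bears on the outcome itself, and the person applying it knows the allocation. A patient who leaves event-free and would have progressed before month 36±6 may be scored event-free. If that happens more often in the intervention arm, its event rate is lowered artificially and the comparison shifts towards benefit. The lack-of-efficacy exit also fits poorly with section 6, which wants patients kept on the intervention even after an endpoint.

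**Working it through.** **1. Is post-exit imaging secured elsewhere?**

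- Section 6.3 says all patients will have a CTA or MRA at 36 (±6) months as standard of care, with images uploaded. It does not name withdrawn patients.
- Section 6.3 also sends subsequent imaging to the core lab, but only imaging during the study period. Section 6 describes a patient's study period by the treatment period (36 to 120 months).
- Section 6.4 retrieves missing images, but at the visit about 30 days after end of treatment, which may be waived. It cannot reach a scan made a year later.
- The permission for further examinations in the 4.6.1 table is optional and concerns ineligible patients.

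Continued imaging is therefore likely in practice, but its collection after withdrawal is not fixed.

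**2. The plan's own figure.** Section 9.1 uses 15% versus 8.25%, alpha 0.05 and power 80%. With mean risk 0.11625, two-sided alpha, pooled null variance and no continuity correction:

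n = [1.960·√(2·0.11625·0.88375) + 0.842·√(0.15·0.85 + 0.0825·0.9175)]² / 0.0675² = 352.8, so 353 per group, as stated. The same normal approximation is used below.

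**3. Risk left after an event-free scan.** Carry-forward loses only events after the last image. Assume a constant hazard giving 15% at 36 months:

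q(t) = 1 − 0.85^((36−t)/36)

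- last scan at month 12: q = 1 − 0.85^(24/36) = 10.3%
- last scan at month 24: q = 1 − 0.85^(12/36) = 5.3%

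These times fit section 7.2.1, which anticipates imaging every one or two years.

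**4. Effect on the test.** Assume 15% true risk in both arms, n = 388 per arm (section 4.1; 0.15 × 388 = 58 expected events each), a share w of the intervention arm leaving event-free through intervention-only exits, and all their later events missed. The observed difference is d = w·q, and

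P(false benefit) ≈ Φ((d − 1.960·SE₀)/SE₁), with SE₀ ≈ SE₁ ≈ 0.0256.

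Example, w = 1% (3.9 patients), scan at month 12: d = 0.00103, 0.40 events lost, d/SE = 0.040, Φ(−1.960 + 0.040) = Φ(−1.920) = 2.7%.

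| w | Last scan | Events lost (388·w·q) | RR (1 − w·q/0.15) | P(false benefit) |
|---|---|---|---|---|
| 0 | – | 0 | 1.00 | 2.5% |
| 1% | month 24 | 0.20 | 0.996 | 2.6% |
| 1% | month 12 | 0.40 | 0.993 | 2.7% |
| 5% | month 24 | 1.02 | 0.98 | 3.2% |
| 5% | month 12 | 1.99 | 0.97 | 3.9% |

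The 1% rows illustrate lack of efficacy alone. The 5% rows show what a larger excess of intervention-arm exits for all three reasons would do. The protocol gives no rate for any of them.

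**5. How many exits for a visible effect?** Three lost events give about 4.9% (RR 0.95). That takes 3/0.103 = 29 withdrawals after a month-12 scan, or 3/0.053 = 57 after a month-24 scan.

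**The case against.** The best defence is that section 4.6.1 describes a treatment stop. Its heading says so, the risk-to-benefit clause speaks of further treatment, and the reasons its table gives for complete study drop-out do not include lack of efficacy. Sections 6.3 and 9.3 speak of all patients and full intention to treat, and exclude nobody. Section 9.4 monitors any subarachnoid haemorrhage, so rupture is less likely to be missed than growth. Section 6 discourages the exit, and a list of possible reasons can coexist with an intended course. This makes continued collection a reasonable reading. It does not make it a rule: the reason list is not stated to be exhaustive, and even a stop of the intervention alone is given a single follow-up.

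A second defence is that failed efficacy would usually be seen as growth on a scan. That stands: growth of at least 1 mm on the last image is an event and is carried forward as one. What remains is the patient withdrawn before the threshold, for instance with smaller growth or an unmet blood-pressure target. For those, sections 4.6.1 and 6.3 offer milder responses: adjusting or stopping one component, or referral to the general practitioner.

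A reader might infer a larger bias by giving withdrawn patients the full 15% risk, or 50%; 1% withdrawn would then yield 2.9% or 3.9%. The documents do not support this. The full 15% requires that no scan after baseline exists, and nothing puts these patients at 50%. A reader might also treat lack of efficacy as the sole problem, but adverse-event and pregnancy exits are equally one-sided and meet the same carry-forward rule.

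**Conclusion.** The point holds as a gap in the withdrawal and collection rules. The protocol states routes out of the study that exist in one arm only, fixes carry-forward for those who take them, and does not clearly require use of standard-of-care scans made afterwards. This weakens the promised intention-to-treat analysis, and any resulting loss that is greater in the intervention arm favours the intervention. A statistical analysis plan cannot repair it, because it cannot recover scans that were not collected.

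The size is unknown and probably small: about 2.6–2.7% false benefit against 2.5% for lack of efficacy alone. This rests on 1% of the arm withdrawn, a last scan at month 12 or 24, constant hazard, and no later scan used. The documents do not show that follow-up certainly stops, that such withdrawals are frequent, or that the primary result is biased. It is worth correcting because the correction costs little.

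**What to change.** Amend section 4.6.1 and its table of terms to state that:

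- any investigator-initiated stop, including for lack of efficacy, ends treatment components only;
- unless the patient withdraws consent, visits or telephone contact, upload of standard-of-care CTA/MRA and central blinded reading continue to the 36±6-month assessment in both arms;
- the last image is carried forward only when no later image exists.

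Delete the lack-of-efficacy item, or define it as a treatment stop consistent with section 6. Deleting it alone is not enough, because the risk-to-benefit clause and the open category of other reasons would still permit the same exit, and the adverse-event and pregnancy exits would remain.

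Cost: a short amendment, a memo to sites, and slightly more follow-up of patients off treatment. No additional patients or trial-specific scans are needed.

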## 5.5 Randomisation

### 5.5.1 Randomisation method

For randomisation an online tool (<https://www.randomizer.at/>) will be used. Any patient included will be 1:1 randomised into one of the two study arms: 1) a strategy with ASA 81 - 100mg/day and intensive blood pressure treatment (targeted systolic blood pressure below 120mmHg) with weekly measurements using a home blood pressure measuring device; or 2) standard of care.

There is no placebo group. Each study centre will be provided with an access code to perform the randomisation independently. Stratification will occur according to centre.

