CTAs/MRAs beyond this time point will also be uploaded to the central server. We will collect data on GFR and blood sodium in patients with pre-existing, compensated chronic renal failure (stage III: GFR <60 mL/min/1.73 m^2), who are monitored for these parameters by their treating physicians. During all trial visits the investigators will stress that smoking cessation is pivotal and inform patients who smoke about possible options for help in smoking cessation. The number of cigarettes per day and alcohol consumption per day will be recorded. The investigator will collect data on GFR and blood sodium in patients with pre-existing, compensated chronic renal failure (stage III), who are monitored for these parameters by their treating physicians.

Any subsequent imaging during the study period will be uploaded to the core lab. Timing and frequency of subsequent CT- or MR examinations vary in clinical practice. In case the 36 ( $\pm 6$ ) months' time point is not sampled in a particular patient, the latest CTA/MRA prior to this date will be analysed. Patients with imaging using different imaging modalities (e.g. initial MRA vs. subsequent CTA) will be excluded from assessing the images for the primary endpoint and considered to be dropouts in the statistical analysis. However, for patients with several images of the same modality, an analysis for the time span between these two identical modalities may be permitted by the adjudication committee.

At each treatment visit, remaining trial medication will be collected, the number documented and the blisters will be sent back for disposal. New trial medication is provided for the next period.

End of treatment visit will be planned 36 months after inclusion of the last patient. The same procedures are performed as in treatment visits. Patients should be asked to continue study participation/ treatment until month 120 ( $\pm 30$  days) or end of study (whatever comes first).

In case of intolerable AEs/ SAEs, new visits will be planned by the investigator until the findings have been clarified or became stable.

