All patients will have a CTA/MRA at least 36 ( $\pm 6$ ) months after randomization and preferably around the last follow-up visit as per standard of care. All images will be uploaded in a pseudonymised manner to a central server. Patients will be told to stop the IMP if there is no indication to continue (indications to continue are for example myocardial infarction, TIA, ischemic stroke), and be advised to visit a general practitioner for future blood pressure regulation. A letter will be sent to the general practitioner that the study has ended.

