#### 7.2.1 Progression-free Survival

Progression-free survival, defined as the time from randomization to the first observation of aneurysm growth or rupture, will be assessed every 12 months, based on available data such as subsequent imaging, until study end. During the course of the study, timing of subsequent imaging of the intracranial aneurysm will be at the discretion of the treating physician, since there are currently no guidelines in this respect. However, we anticipate that many centers will perform imaging every one or two years. If a patient is lost to follow up, progression-free survival is censored at the time of last imaging. No x-ray or other radiation is used for trial purposes only. However, if the patient undergoes examinations for medical reasons (such as routine control of aneurysm) such examinations may be used for a second assessment for trial purposes.

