## 9 STATISTICAL PROCEDURES

### 9.1 Sample Size Calculation

The test of the primary hypothesis is outlined in paragraph 9.4 (Statistical Methods). The sample size calculation is based on the following assumptions:

Previously a hazard ratio of 1.3 (95%CI 1.0-1.9) for hypertension as a risk factor for aneurysm rupture (PHASES cohort) and an odds ratio of 0.27 (95% CI 0.27-0.67) for risk of rupture in patients with unruptured intracranial aneurysms using ASA was reported. If we conservatively assume a risk reduction of 45% for the primary outcome measure and the risk to have a primary outcome event at three years of 15% in the standard treatment group and 8.25% in the intensive treatment + ASA group, an alpha of 0.05 and a power of 80%, 353 patients are needed in each group. Assuming a dropout rate of 10%, we will need to assign 776 patients to the trial so that 706 patients can be analyzed.

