### 9.3 Statistical Methods

Baseline characteristics will be summarized as means with standard deviations or proportions, as appropriate. In the primary analysis we will quantify the treatment effect of a strategy aimed at risk factor modification by intensive blood pressure treatment, monitoring with a blood pressure measuring device, and acetylsalicylic acid (ASA) on the risk of aneurysm rupture or growth, which is an established surrogate for the risk of rupture, compared with standard blood pressure treatment and no ASA.

We will compare the occurrence of outcome events in the two groups in terms of the risk ratio (RR), which will be obtained by means of a Poisson model. The precision of the RR estimates will be described with 95% confidence intervals obtained from the Poisson model. Our primary analyses will be based on the intention-to-treat principle. Patients will be censored in case of death from causes other than aneurysm rupture. In addition to crude analyses, we will do an analysis adjusted for the main risk factors of the primary outcome: aneurysm size, shape, location, age and smoking status. For our secondary analyses in which the timing of the outcome event is not prespecified but all follow-up data are taken into account, we will calculate hazard ratios using Cox regression analyses. Final details will be specified in the Statistical Analysis Plan.

We plan the following subgroup analyses: age ( $\leq 55$  versus  $> 55$  years), sex, and type (with or without previous rupture of another aneurysm), size (1.0-4.0 mm versus  $\geq 4.1$  mm), aneurysm location (posterior communicating artery / anterior communicating artery / posterior circulation versus all other aneurysms) and morphology of aneurysm (regular versus irregular shape).

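### Carrying the last scan forward scores a growth-free early scan as no event at 36 months, so unequal imaging follow-up between arms biases the primary risk ratio

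*Protocol*

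**What the plan says.** The primary outcome is aneurysm rupture, or growth of at least 1 mm on serial imaging, within 36±6 months of randomisation (protocol sections 2.1, 7.2 and 9.1).

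Two passages say what happens when imaging is incomplete:

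- Section 4.6.1, on withdrawal: "In case of early withdrawal, the last aneurysm imaging will be used for the primary outcome analysis". The method is named there as LOCF.
- Section 6.3, for any patient not imaged at 36 (±6) months: "the latest CTA/MRA prior to this date will be analysed".

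Section 9.3 estimates a risk ratio from a Poisson model on the intention-to-treat principle. The only censoring it names for this analysis is death from causes other than rupture. Section 9.2 makes the full analysis set all randomised patients, with narrow exceptions for ineligibility.

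The trial does not fix when scans are taken. Section 7.2.1 says that "timing of subsequent imaging of the intracranial aneurysm will be at the discretion of the treating physician" and expects many centres to image every one or two years. Section 5.6 states that patients and investigators are not blinded. In the same section 7.2.1, progression-free survival is censored at the last imaging when a patient is lost to follow-up.

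**The concern.** Growth can be seen only on a scan taken after it has happened. A patient last scanned at 18 months without growth has been observed for half the risk period, yet enters the 36-month risk ratio as a full non-event. (An early scan that does show growth counts as an event, so the error runs one way within each arm.) The arm with more early last scans therefore shows a lower risk than it has.

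The protocol gives reasons why the arms may differ. Among the withdrawal reasons in section 4.6.1, lack of efficacy of the experimental intervention, intolerable adverse events from both of its components, and failure of self-medication fall wholly or mainly on the intervention arm. Pregnancy and lactation are reasons there too, while control patients who become pregnant explicitly stay in. The table in that section provides for a single follow-up after the intervention is stopped. Blinded central reading protects how each scan is read; it does not correct how long each patient was observed.

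At stake is the validity of the primary comparison. The two formal interim analyses in section 9.4 use the same outcome.

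**Working it through.** **Inputs from the protocol.** Section 9.1 assumes three-year risks of 15% for control and 8.25% for intervention. Section 4.1 gives 776 to be enrolled, that is 388 per arm. Section 5.5.1 sets 1:1 allocation. The size statement in section 9.1 reads: "an alpha of 0.05 and a power of 80%, 353 patients are needed in each group".

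**Assumptions, not in the protocol.** Constant hazard; a share w of an arm has its last scan at 18 months instead of 36; that share is unrelated to the patient's own risk. Rupture after the last scan is treated as missed along with growth. That slightly overstates the effect, because rupture can be known without a scan, but rupture is rare here (section 3.1: 5-year risk usually below 3%).

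**Step 1: reproduce the planned size.** Two-sided test, pooled variance under the null, mean risk (0.15 + 0.0825)/2 = 0.11625:

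n = [1.960·√(2 × 0.11625 × 0.88375) + 0.842·√(0.15 × 0.85 + 0.0825 × 0.9175)]² / 0.0675² = 352.8, rounded up to 353 per group. The stated figure is reproduced.

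**Step 2: risk visible at 18 months.** With 15% at 36 months and a constant hazard, the 18-month risk is 1 − √0.85 = 0.0780. An 18-month scan captures 0.0780/0.15 = 52% of the 36-month risk.

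**Step 3: apparent risk under LOCF.** Apparent risk = 0.15(1 − w) + 0.0780w, which gives:

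- w = 0: 0.1500
- w = 10%: 0.1428
- w = 20%: 0.1356
- w = 30%: 0.1284

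**Step 4: false-positive rate with no true effect, 388 per arm.** Let d be the difference in apparent risk, SE₀ the pooled standard error and SE₁ the unpooled one. The chance of a significant benefit is Φ((d − 1.96·SE₀)/SE₁); the chance of significant harm uses −d. For 10% versus 20%, d = 0.0072 and both standard errors are 0.0248 to 0.0249, giving 4.7% + 1.2% = 6.0% before rounding the parts.

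| Last scan at 18 months, control vs intervention | Apparent ratio | Significant benefit | Two-sided error |
|---|---|---|---|
| 10% vs 10% | 1.00 | 2.5% | 5.0% |
| 10% vs 20% | 0.1356/0.1428 = 0.95 | 4.7% | 6.0% |
| 10% vs 30% | 0.1284/0.1428 = 0.90 | 8.5% | 9.0% |
| 0% vs 30% (worst case) | 0.1284/0.1500 = 0.86 | 13.7% | 14.0% |
| 20% vs 10% (reversed) | 0.1428/0.1356 = 1.05 | 1.2% | 6.0% |

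**Step 5: power under the planned effect, equal incompleteness.** The 18-month risk in the intervention arm is 1 − √0.9175 = 0.0421. Under LOCF all 388 per arm are analysed; the comparator leaves the incomplete patients out.

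| Incomplete in both arms | LOCF, 388 per arm | Incomplete patients excluded |
|---|---|---|
| 0% | 83.6% | 83.6% |
| 10% | 81.6% | 79.6% |
| 20% | 79.5% | 74.8% |
| 30% | 77.2% | 69.0% |

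With equal incompleteness the apparent ratio stays at about 0.55. At the planned 10%, power is kept, and in this setting LOCF costs less than exclusion.

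**The case against.** The best defence is that the arms may not differ much in imaging. Scans are routine care rather than trial visits. Eligibility requires regular monitoring for growth (section 4.4), visit schedules are the same in both arms (section 6.3), a patient who cannot tolerate one component may continue the other (section 4.6.1), and missing images are retrieved at the follow-up visit (section 6.4). This narrows the likely gap, and a modest imbalance does modest harm, as the 10% versus 20% row shows. It does not remove the gap, and the rule gives no protection if one appears.

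Four stronger readings are tempting and should not be pressed.

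- **Loss of power.** Using 353 per arm, 30% incompleteness would seem to bring power down to 73%. But 353 is the size after dropouts are removed, whereas LOCF keeps all 388. The loss comes from absent scans, not from the rule.
- **Baseline-only patients scored event-free.** The protocol does not say so. The endpoint needs two angiographies, while LOCF with an all-randomised set would keep the patient. The case is undefined and needs a sentence; figures that depend on it should not be quoted as the protocol's effect.
- **A contradiction in section 6.3.** It says "All patients will have a CTA/MRA at least 36" (±6) months after randomisation, as per standard of care. Beside the rule for a missed time point, that reads as an expectation with a fallback.
- **A like fault in the secondary analysis.** Section 9.3 states that "we will calculate hazard ratios using Cox regression analyses". Growth is dated at detection, so scan frequency can matter, but a small null simulation (200 runs, annual against biennial scans) gave a hazard ratio of only 0.94 and about 6% rejections.

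**Conclusion.** The point holds as a conditional bias in the primary analysis. The protocol itself fixes LOCF for the primary outcome, so this is not a detail left to the statistical analysis plan, and it scores partly observed patients as fully observed. It also departs from the protocol's own treatment of progression-free survival, which is censored at last imaging.

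The size depends on how unequal the arms are. Under the stated assumptions, two-sided error runs from 5% (equal) through 6% and 9% to 14%, the last only with complete control imaging. The direction follows the less-observed arm: the withdrawal reasons make a false benefit the likelier outcome, but the protocol gives no figure for incompleteness by arm, and less observation of controls would bias against the intervention. A reader might infer that a false benefit is built in, or that the trial is underpowered because of this rule; the documents support neither.

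**What to change.** Remove LOCF as the primary rule from sections 4.6.1 and 6.3, and state in section 9.3 or the statistical analysis plan:

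1. Growth or rupture is analysed with time from randomisation to the last evaluable scan in the model, for example a complementary log-log or grouped-interval model, standardised to a 36-month risk ratio. This agrees with the censoring at last imaging in section 7.2.1.
2. Patients with no evaluable follow-up scan and no rupture are missing, not event-free.
3. LOCF is kept as a sensitivity analysis.

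The cost is wording and some analysis work; section 10.1 already collects the dates and types of subsequent imaging. The statistical price is a somewhat wider interval, an assumption on the shape of the hazard, and reliance on scan timing being non-informative given the covariates. The model corrects for unequal observation time, not for withdrawal that depends on unobserved growth.
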